### **12.1.2 Secondary Efficacy**

Similar to the primary endpoint analyses comparisons will be performed using CMH tests stratified by analysis center. The secondary efficacy endpoints will be:

- Percentage of subjects who show at least a 2 grade improvement and reach Clear to Almost Clear at Week 12 for IDP-122 Lotion verses IDP-122 Vehicle Lotion
- Percentage of subjects who show at least a 2 grade improvement and reach Clear to Almost Clear at Week 6 for IDP-122 Lotion verses IDP-122 Vehicle Lotion
- Percentage of subjects who show at least a 2 grade improvement and reach Clear to Almost Clear at Week 4 for IDP-122 Lotion verses IDP-122 Vehicle Lotion
- Percentage of subjects who show at least a 2 grade improvement and reach Clear to Almost Clear at Week 2 for IDP-122 Lotion verses IDP-122 Vehicle Lotion

Evaluation of the secondary efficacy variables will use a gated sequential procedure starting with the comparisons of the first bulleted item and proceeding onto the next item. The process will terminate if a nonstatistically significant value is observed.

### 12.1.3 Tertiary Efficacy

The follow tertiary efficacy endpoints will be analyzed to further characterize the treatment effect of IDP-122 Lotion over the IDP-122 Vehicle Lotion. The analyses will use CMH testing stratified by analysis center without adjusting for multiplicity.

- Percentage of subjects with at least a 2-grade improvement from Baseline in the score for each of the signs of psoriasis (erythema, plaque elevation, and scaling) at Week 8 for the target lesion
- Percentage of subjects with at least a 2-grade improvement from Baseline in the score for each of the signs of psoriasis (erythema, plaque elevation, and scaling) at Week 12 for the target lesion
- Percentage of subjects with at least a 2-grade improvement from Baseline in the score for each of the signs of psoriasis (erythema, plaque elevation, and scaling) at Week 6 for the target lesion
- Percentage of subjects with at least a 2-grade improvement from Baseline in the score for each of the signs of psoriasis (erythema, plaque elevation, and scaling) at Week 4 for the target lesion
- Percentage of subjects with at least a 2-grade improvement from Baseline in the score for each of the signs of psoriasis (erythema, plaque elevation, and scaling) at Week 2 for the target lesion

### 12.1.4 Pooling Analysis

The clinical study will be conducted under a common protocol for each investigational site with the intention of pooling the data for analysis. Every effort will be made to promote consistency in study execution at each study site. The study is intended to be conducted in a manner such that a minimum of 15 subjects will be randomized and included in the ITT population (i.e., approximately at least 10 subjects in the IDP-122 arm and at least 5 subjects in the Vehicle arm) for any investigator. In the event that there are too few subjects in a treatment arm for an investigator, then the investigator's data will be combined to achieve the desired sample size minimum per treatment arm. The combining of investigator data will be accomplished by taking the investigator with the smallest enrollment and combining it with the investigator with the largest, restricted to investigational sites that did not meet minimum enrollment. If there is a further need to combine data, then the data of the investigator with the second smallest enrollment will be combined with the investigator's data which had the second largest enrollment, and so on. This process will continue for all investigators who did not have a minimum of 15 subjects enrolled. The process of combining investigator data that have insufficient subjects per treatment arm will result in redefining the groups of investigators for the purposes of statistical analyses. These combined groups will be referred to as "analysis centers" in the statistical analyses.

Amendment 1, Clinical Study Protocol, 14 October 2015

CONFIDENTIAL

The consistency of treatment response will be investigated across the analysis centers subsequent to combining the data as described above. Statistical tests will be conducted to identify if there are extreme analysis centers that could affect the interpretation of common statistical and clinical conclusions. For the purpose of testing consistency of treatment response, the primary efficacy variable will be considered. The percent of subjects with treatment success at Week 8 will be analyzed with a logistic regression with factors of treatment group, analysis center, and the interaction term of treatment group by analysis center. Further examination will follow if the analysis results in a significant interaction term.

In the event that the logistic regression interaction p-value is less than or equal to 0.10, a sensitivity analysis that excludes analysis centers with the extreme efficacy result will be performed to determine the robustness of the treatment effect. On the other hand, if the analysis results in an interaction terms with p-value greater than 0.10, then the conclusions from the pooled data will be considered to be free of the impact of extreme analysis centers.

The first step in conducting a sensitivity analysis is to identify the extreme analysis center or centers that contribute to the statistical significance of the interaction term of the logistic regression. The process involves submitting subsets of analysis centers to the logistic regression and observing the interaction p-value for the subset. Subsets resulting in interaction p-values greater than 0.10 are considered homogeneous.

The search for an extreme analysis center begins by analyzing all subsets that can be created by excluding 1 analysis center. If 1 or more of the subsets result in an interaction p-value greater than or equal to 0.10, then the analysis center excluded from the subset with the largest interaction p-value is deemed the extreme analysis center.

If all subset interaction p-values are less than or equal to 0.10, then the process will analyze the interaction for all subsets that can be created by excluding 2 analysis centers. If 1 or more of these subsets generate interaction p-values larger than 0.10, then the analysis centers excluded from the subset with the largest interaction p-value are deemed the extreme analysis centers.

Thus, the process of identifying the extreme analysis centers will continue in a stepwise manner by first excluding 1, then 2, then 3, etc, analysis centers until the logistic regression interaction p-value exceeds 0.10.

Once the extreme analysis center or centers have been identified, then the treatment p-values of the remaining analysis centers will be computed. Inferences will be drawn from the treatment p-value, as well as any pertinent observations regarding the extreme analysis center or centers. Additionally, it is noted that this process excludes subjects from the analysis in a nonrandom manner and has an unpredictable impact on the power of the treatment effect test.

In the event that the treatment effect of the remaining subset is not statistically significant, due consideration of the post hoc aspects of the process will be given when the results are interpreted. Conclusions will be presented by the sponsor as appropriate to the findings of the sensitivity analysis.

Prior to investigating the treatment effect within the analysis centers, the magnitude of the site main effect will be investigated to determine if the main site-to-site variability is such that it could mask the analysis center effects. Thus, prior to pooling, the percent of subjects with treatment success at Week 8 will be analyzed with a logistic regression with factors of treatment group, site, and the interaction term of treatment group by site. If the analysis is not computationally feasible due to some sites having very few subjects enrolled, the low-enrolling sites will be excluded from the analysis.

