**Sample size calculations:**

One hundred forty (140) IDP-122 treated subjects and seventy (70) vehicle treated subjects will have greater than 95% power to detect a statistically significant outcome for a two-sided test with an alpha level of 0.05. This is based on treatment success rates of 33.3% and 9.7% which were observed in V01-118A-201. Success was defined as at least a 2-grade improvement from Baseline in the IGA score and an IGA score equating to "Clear" or "Almost Clear".

This study will be performed in compliance with GCP including the archiving of essential study documents. This protocol follows guidelines outlined by the International Conference on Harmonization (ICH). All data furnished to the investigator and his/her staff, and all data obtained through this study, will be regarded as confidential and proprietary in nature and will not be disclosed to any third party, except for the United States Food and Drug Administration or other regulatory body, without written consent from the sponsor.

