## 12 Statistics

All statistical processing will be performed using SAS® unless otherwise stated. No interim analyses are planned. Except where noted, all statistical tests will be two-sided and will be performed at the 0.05 level of significance.

Descriptive statistics will be used to provide an overview of the efficacy and safety results. For categorical parameters, the number and percentage of subjects in each category will be presented. For continuous parameters, descriptive statistics will include n (number of subjects), mean, standard deviation, median, minimum, and maximum. Appropriate inferential statistics will be used for the primary and secondary efficacy variables.

The primary method of handling missing efficacy data will be the method of Markov Chain Monte Carlo (MCMC) multiple imputation. As a sensitivity analysis, the last observation carried forward method (LOCF) will be used (i.e., the last available on-therapy observation for a subject will be used to estimate subsequent missing data points). No imputations will be made for missing safety data.

A statistical analysis plan (SAP), describing all statistical analyses will be provided as a separate document. The SAP will be finalized prior to unblinding of the study treatments.

Amendment 1, Clinical Study Protocol, 14 October 2015

CONFIDENTIAL

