### **12.1.1 Primary Efficacy**

The primary efficacy endpoint will be used to compare once daily application of IDP-122 Lotion and vehicle.

The percent of subjects with treatment success at Week 8 will be analyzed using Cochran-Mantel-Haenszel (CMH) tests stratified by analysis center.

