### 12.8.2 Sample Size Determination

The following power calculations were computed using the observed Week 8 dichotomized IGA efficacy data in the ITT population from the Phase 2 study V01-118A-201. SAS PROC POWER with the Fisher's exact test option was used to calculate the power for various sample sizes using a two-sided test with an alpha of 0.05. Table 5 presents the efficacy estimates derived from study V01-118A-201.

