**Table 5. Percent Dichotomized IGA Success for Treatment Groups**

	IDP-122* (IDP-118 Monad (HP 0.01%) Lotion)	IDP-122 (IDP-118) ** Vehicle
Percent Success	33.3%	9.7%

Success was defined as at least a 2-grade improvement from Baseline in the IGA score and an IGA score equating to "Clear" or "Almost Clear".

\*IDP-122 refers to the (IDP-118 Monad (HP 0.01%) Lotion) used in the V01-118A-201 Study

\*\*IDP 118 Vehicle composition used in the V01-118A-201 is equivalent to the vehicle that will be used in this study (IDP 122 Vehicle Lotion).

One hundred forty (140) IDP-122 treated subjects and seventy (70) vehicle treated subjects will have greater than 95% power to detect a statistically significant outcome for a two-sided test with an alpha level of 0.05.

It was noted that the estimates extracted from the above studies are based on the LOCF method of handling missing values while the proposed Phase 3 analysis will account for missing values using multiple imputations. The power stated above sufficiently exceeds 95% which will compensate for the difference in handling of missing data.

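### The extreme-center sensitivity analysis takes inference from a p-value in centers selected on outcome, and requires the post hoc caution only when that p-value is not significant

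*Combined protocol and SAP*

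**What the plan says.** The primary test is set in section 12.1.1: "The percent of subjects with treatment success at Week 8 will be analyzed using Cochran-Mantel-Haenszel (CMH) tests stratified by analysis center". Section 12.8.1 makes the ITT set primary for efficacy, and section 12 adds that, except where noted, "all statistical tests will be two-sided and will be performed at the 0.05 level of significance".

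Section 12.1.4 then tests consistency across analysis centers with a logistic regression containing a treatment-by-center interaction. If the interaction p-value is 0.10 or less, "a sensitivity analysis that excludes analysis centers with the extreme efficacy result will be performed to determine the robustness of the treatment effect". The extreme centers are found by trying every exclusion of one center, then of two, then of three and so on, until the interaction p-value exceeds 0.10. At each depth the exclusion giving the largest interaction p-value is chosen, and the number excluded has no cap.

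Four statements govern how the outcome is read:

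- On the basis for inference: "Inferences will be drawn from the treatment p-value, as well as any pertinent observations regarding the extreme analysis center or centers".
- A note that applies whatever the result: exclusion is not random, and its effect on power cannot be predicted.
- A caution limited to one result, where the "treatment effect of the remaining subset is not statistically significant, due consideration of the post hoc aspects of the process will be given".
- A closing sentence that leaves the sponsor to present conclusions in line with the findings.

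**The concern.** A robustness check should be read by the same rule in both directions, fixed in advance. The search is equally post hoc whichever side of 0.05 the remaining-center p-value falls, yet the plan calls for that to be weighed only when the p-value is not significant. A significant all-center result that is lost after trimming therefore meets an explicit caution. A non-significant result that becomes significant after trimming does not.

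The favourable p-value needs the caution as well. Centers are dropped because their observed treatment effects disagree with the rest, so the remaining data are selected on outcome. A CMH p-value computed in them does not keep its nominal 5% level.

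What is at stake is how the trial report describes robustness, and whether a trimmed p-value is cited as inferential support. The primary test is not at stake.

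**Working it through.** **Step 1. The plan's own figure.** Section 12.8.2 states: "One hundred forty (140) IDP-122 treated subjects and seventy (70) vehicle treated subjects will have greater than 95% power". The synopsis gives the rates: "This is based on treatment success rates of 33.3% and 9.7% which were observed in V01-118A-201". The stated method is: "SAS PROC POWER with the Fisher's exact test option was used to calculate the power".

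Normal approximation with 140 and 70 subjects:

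- Pooled rate = (140 × 0.333 + 70 × 0.097) / 210 = 0.2543
- SE under no effect = √[0.2543 × 0.7457 × (1/140 + 1/70)] = 0.0638
- SE under the effect = √[0.333 × 0.667/140 + 0.097 × 0.903/70] = 0.0533
- Power = Φ[(0.236 − 1.96 × 0.0638) / 0.0533] = Φ(2.08) = 98.1%

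Exact enumeration of the two-sided Fisher test gives 98.0%. The stated figure is reproduced.

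**Step 2. What trimming costs in power.** Assume 14 centers of 10 + 5, the section 12.1.4 minimum, and the same formula:

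| Centers kept | Active + vehicle | Power |
|---|---|---|
| 14 | 140 + 70 | 98.1% |
| 13 | 130 + 65 | 97.3% |
| 12 | 120 + 60 | 96.0% |
| 10 | 100 + 50 | 91.9% |
| 8 | 80 + 40 | 84.2% |

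This table ignores selection and shows only the effect of sample size. Some loss of significance is expected even when the effect is the same everywhere.

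**Step 3. The remaining-center p-value with no treatment effect.** The search was simulated with complete data, equal centers, a likelihood-ratio interaction test at 0.10, and CMH on the remaining centers. All percentages are of trials in which the search ran.

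| Assumed setting | Significant, two-sided (nominal 5%) | Favours active (nominal 2.5%) |
|---|---|---|
| 14 centers of 10 + 5 or 7 of 20 + 10; rate 9.7% or 20% in both arms | 14-17% | 1-8% |
| 7, 10 or 14 centers; rates 9.7% to 25%; 8,000 trials per setting | 12-19% | 2.5-11% |
| 14 centers of 10 + 5; rate 20%; 730 searched trials of 3,000 | not tabulated | 9.7% (standard error about 1.1 points) |
| 14 centers of 10 + 5; rate 9.7%; 257 searched trials of 3,000 | not tabulated | 1.6% |

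In the last two rows the all-center CMH test favoured active in 1.4% and 0% of the same trials. Over all trials, searched or not, the all-center CMH size in the second row's settings was 4.5-5.2%, so the primary test behaves as it should.

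Expressed per trial run, at a 20% rate the search ran in 24.3% of trials, and in 8.4% of those a non-significant all-center result became a favourable remaining-center result: 0.243 × 0.084 = 2.0% of all trials.

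**Step 4. The other direction.** The share of searched trials with a significant all-center result and a non-significant remainder was:

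- Planning rates in every center: 2.6% with 14 centers, and 1-10% across 7 or 14 centers.
- Planning rates with assumed between-center logit SDs of 1.0 (active) and 0.5 (vehicle): 5.7%.
- Effect mostly in 3 of 14 centers: 36%.
- Effect only in 2 of 14 centers: 48%.

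The procedure can return a weakening result, most often when a few centers carry the effect. It also does so sometimes when no center differs.

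**The case against.** The strongest case on the other side has four parts.

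- **The primary inference is untouched.** This stands. The analysis is labelled a sensitivity analysis, and nothing lets a trimmed subset replace a failed all-center test. A reader might infer that the trial's type I error is inflated; the documents do not support that.
- **The asymmetry is milder than it looks.** A reader might infer that this analysis can support the primary result but never weaken it, or that an unfavourable remainder is to be discounted. Neither is in the text. Giving due consideration is not an instruction to discount, the closing sentence lets conclusions follow the findings, and Step 4 shows that weakening results occur. The note on nonrandom exclusion does apply to every result. However, it speaks of power and not of false positives, so it does not fill the gap for a favourable p-value.
- **The caution has a proper use where it stands.** A lost p-value may reflect only fewer subjects, as Steps 2 and 4 show. This also stands. It is a reason to keep the caution and extend it, and a reason not to read lost significance as proof that the result depends on the excluded centers.
- **The size depends on choices the plan does not state.** The interaction test is not named, and the likelihood-ratio test triggers too often in cells of 10 + 5 (24% at a common 20% rate, against 10%). With a Wald test in which centers with an empty cell carry no weight, the null search almost never ran: at most 0.005% of trials with 14 centers, and 0.6% with 7 at a 20% rate. The percentages are illustrative. That selection on outcome leaves no valid 5% test does not depend on them.

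Finally, section 12 defers full detail to a separate SAP. A reading rule could be set there, but none appears in the text reviewed.

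**Conclusion.** The concern holds as a defect in the reading rule of a conditional sensitivity analysis. The plan draws inference from a p-value in centers selected on outcome and requires the post hoc caution for only one of its two results, which tilts the robustness reading toward a favourable one.

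With no true effect, and only among trials where the search runs, that p-value was significant two-sided in about 14-17% instead of 5%. It favoured active in about 1-8% instead of 2.5%, with 11% the highest value in any setting tried. At the low end there is no excess in favour of active. These figures assume 7 to 14 equal centers, complete data, common rates of 9.7% to 25%, and a likelihood-ratio interaction test. How often the search runs at all depends heavily on that last choice.

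The primary ITT CMH test and its error rate are unchanged. The change is worth making because it is specific and nearly free.

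**What to change.** In section 12.1.4, or in the SAP before unblinding, replace the sentence that draws inferences from the remaining-center p-value and the one-directional caution with:

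*The all-center ITT CMH result is the basis for the efficacy conclusion. The remaining-center result is descriptive. It is reported as an estimate with a confidence interval, beside the all-center estimate and the results of the excluded centers. It carries the post hoc caveat (selection of centers on outcome, reduced sample size) whichever way it falls.*

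Do not add a rule that the report must declare the result dependent on the excluded centers whenever significance is lost. With the planning effect in every center, 1-10% of searched trials lost significance without any such dependence.

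The cost is a few sentences, with no added data or subjects. The sponsor can no longer cite a favourable trimmed p-value as inferential support.

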## **9 Treatment Plan**

### **9.1 Methods of Assigning Subjects to Treatment Groups**

This is a double-blinded study, in which the identity of the study drug will be unknown to investigator/evaluator and subjects, as well as all individuals closely associated with the study.

Subjects will be randomized to 1 of the 2 study drug groups in a ratio of 2:1 (IDP-122 [HP 0.01%] Lotion: IDP-122 Vehicle Lotion). Each screened subject will be assigned a unique 6-digit study subject number assigned by the investigational center, which will consist of the 3-digit investigational center/site number (pre-assigned by sponsor/designee) and the 3-digit chronological screening order number, starting with 001 (e.g., 101001, 101002). The study drug kit will be assigned to subjects based on a randomization code and kits will be dispensed to the subjects at Baseline. A study drug log will document the inventory and dispensing of study drug at each investigational center.

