### **9.2 Randomization and Blinding**

The study drugs will be packaged and labeled identically, and the study drug kits will be numbered sequentially and dispensed randomly to the subjects entering the study within each investigational center. Study drug supplies will be distributed to the investigational centers to maintain the randomization ratio within each investigational center.

As a double-blinded study, the investigators, the site staff, the sponsor, and the clinical monitors will not be aware of the treatment assigned to the individual study subjects.

Delegated staff members at each investigational center will dispense the study drugs and will collect all used and unused study drug containers as scheduled.

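### Section 12.1.4: at the plan's own rates the treatment-by-center logistic models will almost surely have infinite estimates, so the 0.10 consistency rule hangs on an unnamed test, and excluding small sites does not cure it

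*Combined protocol and SAP*

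**What the plan says.** Section 12.1.4 (Pooling Analysis) sets out two logistic models for Week 8 treatment success.

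- **Analysis-center model.** After small sites are merged, success is "analyzed with a logistic regression with factors of treatment group, analysis center, and the interaction term of treatment group by analysis center". An interaction p-value of 0.10 or less starts a stepwise search that removes centers until the interaction p-value exceeds 0.10. A p-value above 0.10 leads the plan to regard the pooled conclusions as unaffected by outlying centers.
- **Site model.** Before merging, the same model is fitted with site in place of analysis center, to look at site-to-site variability. No threshold or action is attached to it. If it is "not computationally feasible due to some sites having very few subjects enrolled, the low-enrolling sites will be excluded from the analysis".

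The enrollment target per investigator is "approximately at least 10 subjects in the IDP-122 arm and at least 5 subjects in the Vehicle arm". Section 9.2 adds: "Study drug supplies will be distributed to the investigational centers to maintain the randomization ratio within each investigational center".

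The protocol does not say whether the interaction p-value comes from a Wald, likelihood-ratio or other test. It does not say what happens when an arm within a center has no successes. Section 12 refers full statistical detail to a separate SAP, whose text is not among the documents available here.

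**The concern.** With treatment, center and their interaction in the model, each arm within each center gets its own fitted success rate. If an arm has 0% or 100% success, its log odds has no finite maximum-likelihood estimate. The plan treats computational failure as a matter of small sites, yet with a vehicle success rate near 10% a center of exactly the planned size will usually have an empty vehicle cell.

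What is at stake is the consistency statement. The 0.10 rule turns one p-value into either a search for outlying centers or a declaration that there are none. With infinite estimates, different tests of the same model give very different p-values, so the conclusion could depend on which statistic is read from the output.

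**Working it through.** **Inputs.** Success rates: "This is based on treatment success rates of 33.3% and 9.7% which were observed in V01-118A-201" (Synopsis, sample size). Allocation 2:1 (9.1), held within center (9.2). About 15 subjects per center and 12-16 centers (Synopsis), hence about 10 active and 5 vehicle per center; 14 x 15 = 210.

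**The plan's own figure.** 12.8.2 states: "One hundred forty (140) IDP-122 treated subjects and seventy (70) vehicle treated subjects will have greater than 95% power". Two-sided Fisher power by exact enumeration at 33.3% vs 9.7% is 98.0% (98.1% by the pooled normal approximation). The plan's figure is reproduced.

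**Chance of an infinite estimate in one center of 10/5.**

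- No success among 5 vehicle subjects: (1 - 0.097)^5 = 0.903^5 = 0.600.
- Adding all-success vehicle cells and all-failure or all-success active cells: 0.607.

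**Across centers.** P(at least one) = 1 - (1 - s)^k, where s is the chance per center and k the number of centers.

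- 14 centers of 10/5: expected number affected 14 x 0.607 = 8.5; P(none) = 0.393^14 = 2.1 in a million, so over 99.99% have at least one.
- 7 pooled centers of 20/10: s = 0.361; 1 - 0.639^7 = 95.6%.
- 14 centers of 10/5 at other vehicle rates: 99.98% at 15%, 99.7% at 20%, 94% at 30%, 78% at 40%.

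**Does excluding small sites help?** If every site enrolls its planned 15, no site is low-enrolling and nothing changes. I also simulated uneven enrollment over 12-16 sites (assumptions: Dirichlet weights with shape 4; between-site SD of 0 or 0.7 on the logit scale). Dropping every site below 15 still left 97-98% of datasets with an infinite estimate. Applying the plan's merging rule instead left 99.7-100%.

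**What the 0.10 rule then does.** Simulated trials with 14 centers of 10/5. Rates are active vs vehicle; all centers have the design rates unless stated.

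| Setting | Wald p <= 0.10 | Likelihood-ratio p <= 0.10 |
|---|---|---|
| No interaction, 33.3% vs 9.7% | 0 of 4,000 | about 9% |
| One center reversed, 0% vs 80% | 0 of 2,000 | 98-99% |
| One center reversed, 9.7% vs 60% | 0 of 2,000 | 70-73% |
| No interaction, 33.3% vs 15% | not tabulated | 16% |
| No interaction, 33.3% vs 20% | not tabulated | 21-24% |

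For Wald, infinite logits were held at a large finite value (an assumption); the result was the same for every value tried. The mechanism is that an empty cell has a huge standard error, so its center gets almost no weight, while the statistic is still referred to 13 degrees of freedom.

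An exact test of equal odds ratios (Zelen's test, by conditional Monte Carlo) triggered in about 11-12% of trials with no interaction. With 400 trials the standard error is about sqrt(0.115 x 0.885 / 400) = 1.6 points, so this is near nominal. It detected the two reversed centers in 96% and 68% of trials.

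**Layout matters for Wald.** With 7 analysis centers of 20/10, Wald triggered in 45-48% of trials for the 9.7% vs 60% center.

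**The case against.** A reader might infer that the procedure cannot work at all. The documents do not support that.

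- **An infinite estimate is not a missing p-value.** The likelihood-ratio test of the planned model stays finite. At the design rates it is close to nominal and detects reversed centers about as well as the exact test. The protocol nowhere specifies Wald. This stands. What remains is that the protocol does not specify likelihood-ratio either, and that test's false-trigger rate roughly doubles once the vehicle rate reaches 20%.
- **It is too strong to say that a Wald test can never start the search.** Merging can produce larger analysis centers, and with 20/10 centers Wald does trigger for some patterns. This stands; the near-zero rate belongs to the 10/5 layout, which is the planned one.
- **The exclusion rule belongs to a model that decides nothing.** The site model looks at site variability; the 0.10 rule uses the analysis-center model. This stands, and the two need different fixes. Beyond merging sites, the analysis-center model has no fallback.
- **The consequence is limited.** The rule leads to a sensitivity analysis that 12.1.4 itself describes with caution, and the separate SAP may name the statistic. Both are fair. The false all-clear under Wald would still be a stated conclusion of the plan.

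**Conclusion.** The point holds in a bounded form. At the plan's rates and center size, about 60% of centers will have no vehicle success, and at least one infinite estimate in the 12.1.4 interaction models is almost certain: over 99.99% with 14 centers of 10/5, about 96% with 7 of 20/10. Excluding low-enrolling sites does not cure this, because the cause is few vehicle successes at the planned center size. The outcome of the 0.10 rule therefore depends on a test the protocol does not name. A Wald test at the 10/5 layout would essentially always report consistency, even with one reversed center. A likelihood-ratio test is sound at the design rates but triggers falsely about 20-25% of the time at vehicle rates near 20%.

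This rests on a vehicle rate near 9.7%; the chance of infinite estimates falls as the rate rises well above 20%. The simulations used complete Week 8 data.

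A reader might infer that the primary result is at risk. It is not: the primary CMH test stratified by analysis center (12.1.1) does not use these models. This is a correction worth making before unblinding, not a flaw in the main comparison.

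**What to change.** 1. **Analysis-center consistency test and subset search (12.1.4).** Replace the logistic interaction p-value with an exact test of equal odds ratios (Zelen's test), and use the same p-value throughout the search. At minimum, prespecify a test that is robust to empty cells and is not Wald.
2. **Imputed data.** State how that test is applied to the multiply imputed Week 8 data of 12.1.5, for example how p-values are combined or whether observed data are used.
3. **Pre-pooling site model (12.1.4, last paragraph).** Do not substitute Zelen's test here: it conditions on each site's total successes and so cannot measure site variability. Use a method that tolerates empty cells, such as Firth penalized likelihood, in place of the rule excluding low-enrolling sites.

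The cost is protocol and SAP wording and a program change before unblinding, with no effect on subjects or data collection. The downsides are somewhat more computing in the subset search, and that centers with no successes in either arm add no information to the exact test.
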